3. DLQI
4. ItchyQoL
5. Leuven Itch Scale
6. Static Participant Global Assessment of Itch Severity (sPGAIS)
7. Participant Global Impression of Change in Itch Severity (pGICIS)
8. Caregiver Global Impression of Change in Itch Severity (cGICIS)
9. PROMIS scales – Pediatric versions for participants <18y
10. Itch Controlled Days Questionnaire

If a participant is unable to access REDCap, these questionnaires will be administered over the phone. Instruments requiring visual analog scale (VAS), such as the Leuven Itch Scale, will be mailed, faxed, or emailed to enable the participant to physically complete the VAS.

9.C.iv. Reminders and Instructions:

Participants will be reminded to comply with completing their itch journals and medication.

Participants will be instructed to mail back their month 1 itch diaries once they receive their new itch diaries (not applicable if participant has chosen to utilize a REDCap based online diary). Additional medication will be dispensed pending acceptable safety labs and mailed to participants along with new Month 2 itch diaries (if participant has chosen physical diary). Participants will be asked to set aside any medication from their month 1 medication bottle and seal the bottle to be returned at their next visit and begin month 2 treatment from the new bottle.

9.D. Month 2 Study Visit:

At 60 days following initiation of study medication (+/- 14 days), participants will return to Stanford for a follow up clinic visit.

Participants will be queried for any adverse events and changes to concomitant medications or wound dressing regimen. These will be assessed by investigators. Menstrual diaries will be collected and reviewed. Participants will be asked to submit their nightly itch diary (NRS), along with any unused medications from the prior two months of treatment for assessment of medication adherence.

Participants will specifically be asked about any symptoms of adrenal insufficiency (e.g. fatigue, abdominal pain, dizziness, etc.). Participants who report symptoms concerning for adrenal insufficiency will be evaluated with instructions to follow-up urgently with their primary care provider for further evaluation, which should include an AM cortisol. If this is abnormal, the participant will be referred urgently to endocrinology for further evaluation including cosyntropin stimulation testing.

Female participants will again be queried regarding abnormal vaginal bleeding (new and different from any related to any known EB wounds in the genital area), new breast findings (not related to EB wounds) and vaginal discharge. If any of these concerns are identified, the woman will be referred to their primary care provider for evaluation.

Vital signs (including weight) will be recorded. Physical examination will be performed.

9.D.i. Wound Assessments:

Participants will be reminded of the location of their target wound(s). Target wounds will be photographed. Participants will evaluate the following characteristics of each target wound: average itch in past 24 hours (NRS), worst itch in past 24 hours (NRS), average pain in past 24 hours (Wong Baker FACES Pain Scale).

If the participant's most pruritic wounds did not meet initial criteria for inclusion as target wounds, we will ask participants to evaluate wound characteristics of these same wounds evaluated at Screening.

Participants and caregivers will be asked about their perceived change in wound size for each target wound and for perceived change in total wound number.

9.D.ii. Global Pruritus Assessments:

The following questionnaires will be completed:

- 1) Stanford EB Itch Survey
- 2) Itch Man
- 3) Dermatology Quality of Life Index (DLQI)
- 4) ItchyQoL
- 5) Leuven Itch Scale
- 6) Static Participant Global Assessment of Itch Severity
- 7) Participant Global Impression of Change in Itch Severity
- 8) Caregiver Global Impression of Change in Itch Severity
- 9) PROMIS scales – Pediatric versions for participants <18y
- 10) Itch Controlled Days Questionnaire

9.D.iii. Electrocardiogram:

Electrocardiogram (ECG) will be performed, using our established technique using non-stick pads to prevent injury due to electrodes. The overall ECG assessment (abnormal or normal) will be summarized and changes from baseline will be descriptively characterized.

9.D.iv. Safety Laboratory Assessments:

Safety labs will again be assessed:

- 1) Complete blood count (CBC)
- 2) Complete metabolic panel (CMP)
- 3) Urinalysis
- 4) Urine pregnancy test (if applicable)
- 5) Thyroid stimulating hormone (TSH)
- 6) Free T4

- 7) Cortisol
- 8) ACTH
- 9) Prolactin

Labs will ideally be drawn in the morning. At the discretion of the investigator, labs drawn by non-study providers within this time window (2 months after medication initiation, +/- 10 days) may be substituted for the study lab draw, as long as they include the same studies of interest. This is in order to reduce unnecessary skin trauma and a potentially psychologically traumatic blood draw.

Any abnormal labs will be reviewed by investigator and appropriate follow-up will be initiated as needed.

Any clinically significant abnormalities identified in prolactin or thyroid function will be followed until the level returns to baseline or appropriate follow-up can be established with a local provider.

9.D.v. Reminders and Home Diaries:

Participants will be given new daily itch diaries to complete during the wash-out period. They will be reminded to continue to complete their daily diary entries.

Female participants of childbearing potential (including participants that have not yet undergone menarche) who are not using hormonal contraception will be provided with a menstrual diary to complete.

Female participants of childbearing potential will be reminded to continue their acceptable form of contraception until 2 weeks after study drug discontinuation.

9.E. Month 3 Phone Call / End of Wash Out Phase:

One month (30 days, +/- 14 days) after completing the double-blind phase participants will be contacted by phone.

9.E.i. Assessments by Phone:

Participants will be queried for any adverse events and changes to concomitant medications or wound dressing regimen. These will be assessed by investigators. Participants will specifically be asked about any symptoms of adrenal insufficiency (e.g. fatigue, abdominal pain, dizziness, etc.).

Female participants will specifically be queried regarding abnormal vaginal bleeding (new and different from any related to any known EB wounds in the genital area), new breast findings (not related to EB wounds), expulsion of an intrauterine device or implant, or vaginal discharge. If any of these concerns are identified, the participant will be referred to their primary care provider for further evaluation.

9.E.ii. Global Pruritus Assessments by REDCap:

A link will be sent to the participant to complete the following assessments via REDCap:

1. Stanford EB Itch Survey
2. Itch Man

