- 7) Cortisol
- 8) ACTH
- 9) Prolactin

Labs will ideally be drawn in the morning. Participants with low cortisol will be referred to their primary care physician or endocrinologist for further evaluation which may include AM cortisol level or dynamic testing with a standard cosyntropin stimulation test. If prolactin is abnormal, participants will be required to have this evaluated prior to study participation.

At the discretion of the investigator, labs drawn by non-study providers within 60 days of screening and baseline may be substituted for the trial screening labs so long as they include the same studies of interest. This is in order to reduce unnecessary skin trauma and a potentially psychologically traumatic blood draw.

9.A.v. Home Diaries and Preparation for Month 1:

Participants will be asked to complete a daily itch diary with their average itch score (NRS) over the past 24 hours and their itch score during dressing changes or bathing (NRS). This may either be an online diary (administered securely through REDCap¹¹) or a paper diary, based on participant preference.

Female participants of childbearing potential (including participants that have not yet undergone menarche) who are not using hormonal contraception will be provided with a menstrual diary to complete.

Participants will be provided with a lab requisition form to have their Month 1 labs drawn at a Quest lab near their home.

Participants will also be specifically educated about the signs and symptoms of adrenal insufficiency (e.g. fatigue, abdominal pain, dizziness, etc.) and will be instructed to report these symptoms to study investigators.

9.B. Baseline Visit (Within 30 Days of Screening):

Participants will return to Stanford for a baseline visit within 30 days of screening. Per the discretion of the investigator(s), screening and baseline may be combined into the same visit. Outside of this window, participants will be considered a “screen fail” and would have to undergo another screening visit.

9.B.i Eligibility Confirmation and Randomization:

Vital signs, medical history, concomitant medications, ECG results, and safety lab results obtained at screening will be reviewed for eligibility. Once participant eligibility is confirmed, randomization will occur.

9.B.ii. Assessments:

Target wounds will again be characterized and photographed. The study diary will be reviewed to assess participants’ mean daily pruritus rating and variation of itch scores at baseline.

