If the baseline and screening visit are combined, participants will be instructed to complete a minimum of 7 days of their nightly itch diary prior to starting medication in order to establish baseline itch severity.

Study medication will be dispensed one week after eligibility is confirmed to reduce confusion about when to begin study medication.

The scheduling of the Month 1 phone call will account for this 1-week lag prior to starting medication.

9.C. Month 1 Phone Call:

Month 1 phone call will occur 30 days after starting the study medication, +/- 14 days.

9.C.i. Safety Laboratory Assessments:

Safety labs will be drawn as early as 10 days prior to scheduled phone follow-up at month 1 following initiation of active treatment. Labs will be drawn at a local laboratory convenient for the participant. They will have the option to have labs drawn at Stanford if they prefer.

At the discretion of the investigator, labs drawn by non-study providers within this time window (1 month after medication initiation, +/- 10 days) may be substituted for the study lab draw, as long as they include the same studies of interest. This is in order to reduce unnecessary skin trauma and a potentially psychologically traumatic blood draw.

Safety labs will include:

- 1) Complete blood count (CBC)
- 2) Complete metabolic panel (CMP)
- 3) Urinalysis
- 4) Urine pregnancy test (if applicable)

Medication will not be sent until safety labs have been reviewed by the investigator. Any abnormal labs will be reviewed by investigator and appropriate follow-up will be initiated as needed.

9.C.ii. Assessments by Phone:

Participants will be queried for any adverse events and changes to concomitant medications or wound dressing regimen. These will be assessed by investigators.

Participants will specifically be asked about any symptoms of adrenal insufficiency (e.g. fatigue, abdominal pain, dizziness, etc.). Participants who report symptoms concerning for adrenal insufficiency will be evaluated with instructions to follow-up urgently with their primary care provider for further evaluation, which should include an AM cortisol. If this is abnormal, we will coordinate with their primary care provider for urgent referral to endocrinology for further evaluation including cosyntropin stimulation testing.

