Appendix: Schedule of Events Table

	Screening		Double-Blind Phase				Optional Open-Label Phase				
	Pre-Screening	Screening	Baseline	Month 1	Month 2	Month 3	Baseline	Month 1	Month 3	Month 6 ¹⁵	Month 12 ¹⁵
	Phone Call	Clinic Visit	Clinic Visit	Phone Call	Clinic Visit	Phone Call	Phone Call	Phone Call	Phone Call	Phone Call	Phone Call
Informed Consent		X									
Demographics	X	X									
Medical History	X	X									
Medication Review	X ¹	X ¹	X	X	X	X	X	X	X	X	X
Review Inclusion / Exclusion Criteria	X	X	X								
Vital Signs ²		X	X		X						
Physical Examination		X	X		X						
Electrocardiogram (ECG)		X			X						
Target Wound Selection		X									
Target Wound Photographs ³		X	X		X						
Target Wound Assessments ⁴		X	X		X						
Questionnaire Completion ⁵		X	X	X ⁶	X ⁶	X ⁶	X ⁶	X ⁶	X ⁶	X ⁶	X ⁶
Dispense Study Diary(ies) ⁷		X	X	X	X ¹⁴	X	X	X	X		
Safety Laboratory Assessments ^{8, 9}		X ¹⁰		X ¹¹	X ¹⁰	X ^{10,11}	X ^{10,11}	X ¹¹	X ^{10,11}	X ¹¹	X ^{10,11}
Determination of Eligibility ¹²			X								
Randomization			X								
Dispense Study Medication or Placebo			X	X							
Dispense Serlopitant						X ¹⁴	X	X	X	X	
Review Adverse Events			X	X	X	X	X	X	X	X	X
Review Study Diary(ies)			X	X	X	X	X ¹³	X ¹³	X ¹³	X ¹³	X ¹³

1: Includes a review of all medications taken within the previous 30 days

2: Includes height, weight, blood pressure, heart rate, temperature

3: Photographs only if participant has target wounds and has given consent for photography

4: Target wound assessment includes: average itch in past 24h, worst itch in past 24h, average pain in past 24h

5: Questionnaires include: Stanford EB Itch Survey, ItchMan, DLQI, ItchyQoL, Leuven Itch Scale, sPGAIS, PROMIS scales (pediatric versions for participants <18y), Itch Controlled Day Questionnaire.

6: Will also assess participant (pGICIS) and caregiver (cGICIS) impression of change in itch severity

7: Either electronic REDCap diary or paper diary. Completed paper diaries will be mailed back to Stanford; new paper diaries will be mailed to participant. Females of childbearing potential not on hormonal contraception will be given a menstruation diary in addition to the study diary.

8: Labs include: CBC, CMP, UA, UPT (if female of child-bearing potential)

9: Labs obtained from outside providers up to 60 days prior to Screening can be used as Screening labs for study purposes. as long as they contain the equivalent labs of interest

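### For paper-diary participants, 9.C.iv mails the Month 2 diary with a drug resupply that waits for acceptable labs, and no text covers the diary when drug is late or held

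*Combined protocol and SAP*

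**What the plan says.** Participants choose how to keep the daily diary. Section 9.A.v says "This may either be an online diary (administered securely through REDCap", or on paper by preference. They are asked to "complete a daily itch diary with their average itch score (NRS) over the past 24 hours".

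For the second blinded month, 9.C.iv says "Additional medication will be dispensed pending acceptable safety labs and mailed to participants along with new Month 2 itch diaries", with the limit "if participant has chosen physical diary". Section 9.C.i adds: "Medication will not be sent until safety labs have been reviewed by the investigator". Section 9.C sets the timing: "Month 1 phone call will occur 30 days after starting the study medication, +/- 14 days". Section 9.C.iv also says "Participants will be instructed to mail back their month 1 itch diaries once they receive their new itch diaries".

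The Schedule of Events in the Appendix has a diary-dispensing row, separate from the row for blinded medication, with an entry at Month 1. Its footnote 7 says "new paper diaries will be mailed to participant" and mentions neither labs nor drug.

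The primary endpoint (section 7) is a fall of at least 3 points in average daily NRS at the end of the two-month blinded phase. Section 9.D places the Month 2 visit at day 60, plus or minus 14 days, and collects the diary there. Section 10.C promises an intention-to-treat analysis and gives no rule for missing scores.

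**The concern.** An intention-to-treat comparison needs outcomes from everyone randomised, whether or not they are still taking drug. If the form that records the outcome travels in the drug parcel, a participant whose resupply is delayed or withheld may also stop recording itch. The reason for the missing scores would then be a lab result or a drug hold, which is not plausibly random.

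A hold is foreseeable. The Month 1 labs in 9.C.i include a urine pregnancy test, and 11.B lists pregnancy among the reasons to stop study drug. Stopping drug is not the same as leaving the study, yet no text keeps such a participant on the diary.

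With 40 participants and no stated dropout allowance in 10.B, a few lost end-of-phase values would matter.

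**Working it through.** **Routes for the Month 2 paper diary**

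| Place | What it provides | Condition |
|---|---|---|
| 9.C.iv | Diary mailed together with drug | Drug waits for acceptable labs |
| 9.C.i | Hold pending lab review | Names medication only |
| Schedule, diary row and footnote 7 | New paper diary at Month 1, by mail | None stated |
| 9.G.i | Diary review and questionnaires at early termination | Participant is leaving the study |

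Only 9.C.iv describes how the parcel is made up. The Schedule allows a separate mailing but does not say that the diary goes when drug does not.

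**Late parcel**

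- Local labs may be drawn up to 10 days after the target date (Schedule, footnote 11): 30 + 10 = day 40.
- The Month 1 call may fall as late as 30 + 14 = day 44.
- If the first paper diary covers 30 days (an assumption; no length is given), the gap is up to 44 − 30 = 14 days plus mailing time.
- With the Month 2 visit on day 60, 60 − 44 = 16 days remain, less mailing time. End-of-phase entries would usually survive.
- At the extreme, the visit may fall on day 60 − 14 = 46, two days after the latest call, and a parcel could miss it.

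**Held parcel**

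If drug is not released and staff follow 9.C.iv literally, no Month 2 paper diary is sent and the end-of-phase diary scores are absent.

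**What lost values would do to power**

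Inputs from 10.B: 20 per arm, responder rates 50% and 10%, one-sided Fisher's exact test. Alpha is not stated; 5% is assumed. Power is the sum, over all tables with one-sided p ≤ 0.05, of Bin(a; 20, p1) × Bin(b; 20, p2).

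- The plan's own figure: 20 per arm gives 83.7%, and the smallest size reaching 80% is 19 per arm (81.4%). The stated total of 40 for 80% power is reproduced to within 2 participants. The plan's 10/20 versus 2/20 table gives a two-tailed p of 0.0138 (stated as 0.01).
- One lost per arm, counted as non-responder: 0.50 × 19/20 = 0.475 and 0.10 × 19/20 = 0.095. Power is 80.7%.
- Two lost per arm: 0.50 × 18/20 = 0.45 and 0.10 × 18/20 = 0.09. Power is 77.3%.
- If lost participants are dropped instead, power is 81.4% (19 per arm) or 78.3% (18 per arm).
- Against placebo at 2/20, the one-sided p is 0.007 for active 10/20, 0.032 for 8/20 and 0.064 for 7/20. The planned result would stop being significant if three active responders had no end value.

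These numbers show the sensitivity of a 40-participant trial to any missing end value. They do not estimate how often this route would cause one.

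**The case against.** The case against is substantial, and most of it limits the point.

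- A reader might infer that the diary can go out only with drug. The text does not say so. Both lab conditions, in 9.C.i and 9.C.iv, attach grammatically to medication, and the Schedule lists the diary separately. Staff could properly mail it alone.
- A reader might infer that late drug means a lost primary endpoint. The endpoint sits at the end of month 2 and a delay falls at its start. Participants also keep the Month 1 diary until the new one comes, although nothing says whether it has spare pages.
- A reader might infer that the diary is the stated source of the primary endpoint. It is the natural source: it records the daily average, supplies the baseline when screening and baseline are combined (9.B.ii), and is collected at Month 2. Apart from it, the only NRS ratings that 9.D spells out are wound-specific. But the plan never names the source, and the items of the Stanford EB Itch Survey are not given.
- A reader might infer bias between arms. Nothing shows that lab holds would differ by arm. The Month 1 panel omits the endocrine tests, and section 5 reports good tolerability and no new safety signals in the pilot.
- Permanent loss needs a paper diary, drug that is not released, and no diary sent separately. The documents give no rate for any of these.

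What stands is that 9.C.iv, followed as written, puts diary and drug in one parcel, and no text provides for the diary when the parcel is late or held. The early-termination visit does not fill the gap: it serves people leaving the study and does not give an end-of-phase value.

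**Conclusion.** The point holds for paper-diary participants and is minor. Section 9.C.iv makes outcome collection in month 2 depend on drug release, and it is out of line with the Schedule. A late parcel would mainly cost early month 2 scores and so affect the weekly-change secondary endpoints. A held parcel could cost the end-of-phase scores, and because that loss follows drug status it undermines the intention-to-treat analysis. It does not defeat it: analysis by assigned arm remains possible, and the absence of a missing-data rule is a separate weakness.

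The size cannot be estimated from the documents. The power figures rest on an assumed one-sided 5% level, on equal loss of 1 or 2 participants per arm, and on counting them as non-responders. The loss of one per arm still leaves power above the stated 80%; the loss of two does not. The planned sample size itself is not in question.

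**What to change.** Either issue paper diaries for both blinded months at first dispensing, or mail the Month 2 diary on a fixed day whatever the lab result or drug status. Reword 9.C.iv so that only the medication waits for the labs, and align it with the diary row and footnote 7 of the Schedule. Tell participants to continue the diary if drug is held or stopped. The rule on when drug is released need not change.

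The cost is a sentence or two of text and either earlier printing or one separate mailing for participants on paper.

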3. DLQI
4. ItchyQoL
5. Leuven Itch Scale
6. Static Patient Global Assessment of Itch Severity (sPGAIS)
7. Patient Global Impression of Change in Itch Severity (pGICIS)
8. Caregiver Global Impression of Change in Itch Severity (cGICIS)
9. PROMIS scales – Pediatric versions for participants <18y
10. Itch Controlled Days Questionnaire

If a participant is unable to access REDCap, these questionnaires will be administered over the phone. Instruments requiring visual analog scale (VAS), such as the Leuven Itch Scale, will be mailed, faxed, or emailed to enable the participant to physically complete the VAS.

9.E.iii. Safety Laboratory Assessments:

Safety labs will again be assessed:

- 1) Complete blood count (CBC)
- 2) Complete metabolic panel (CMP)
- 3) Urinalysis
- 4) Urine pregnancy test (if applicable)
- 5) Thyroid stimulating hormone (TSH)
- 6) Free T4
- 7) Cortisol
- 8) ACTH
- 9) Prolactin

Labs will ideally be drawn in the morning. At the discretion of the investigator, labs drawn by non-study providers within this time window (30 days, +/- 10 days) after completing the double-blind phase may be substituted for the study lab draw, as long as they include the same studies of interest. This is in order to reduce unnecessary skin trauma and a potentially psychologically traumatic blood draw.

Any abnormal labs will be reviewed by investigator and appropriate follow-up will be initiated as needed.

Any clinically significant abnormalities identified in prolactin or thyroid function will be followed until the level returns to baseline or appropriate follow-up can be established with a local provider.

9.F. Continuation of Optional Open Label Phase:

Participants who are eligible for the Open Label Phase in the opinion of the investigators (taking into consideration participant's prior documented adverse events, current medical status, and adherence to trial protocol) and who elect to participate in the Open Label Phase will then be mailed serlopitant 5mg tablets as well as a new study diary to be completed weekly.

This extension phase will be 12 months for participants enrolled prior to May 2020, and 3 months for participants enrolled after May 2020, due to drug availability.

Participants who elect to participate in the open label study (who enrolled prior to May 2020) will undergo open label study phone visits at Baseline, Open Label Month 1, Open Label Month 3, Open Label Month 6, and Open Label Month 12.

Participants who elect to participate in the open label study (who enrolled after May 2020) will undergo open label study phone visits at Baseline, Open Label Month 1, and Open Label Month 3.

9.F.i. Safety Laboratory Assessments:

The safety labs obtained for the Month 3 visit may be used as baseline labs for the Open Label Phase, as long as the labs are drawn within 4 months of the open label baseline visit. Safety labs will be drawn as early as 10 days prior to scheduled phone follow-ups. Labs will be drawn at a local laboratory convenient for the participant. They will have the option to have labs drawn at Stanford if they prefer.

Safety labs will include:

- 1) Complete blood count (CBC)
- 2) Complete metabolic panel (CMP)
- 3) Urinalysis
- 4) Urine pregnancy test (if applicable)
- 5) Thyroid stimulating hormone (TSH)
- 6) Free T4
- 7) Cortisol
- 8) ACTH
- 9) Prolactin

Serlopitant will not be sent until safety labs have been reviewed by the investigator. Any abnormal labs will be reviewed by investigator and appropriate follow-up will be initiated as needed.

9.F.ii. Assessments by phone:

Participants will be queried for any adverse events and changes to concomitant medications or wound dressing regimen. These will be assessed by investigators. Participants will specifically be asked about any symptoms of adrenal insufficiency (e.g. fatigue, abdominal pain, dizziness, etc.). Participants who report symptoms concerning for adrenal insufficiency will be instructed to follow-up urgently with their primary care provider including an AM cortisol assessment. If this is abnormal, we will coordinate with their primary care provider for urgent referral to endocrinology for further evaluation including cosyntropin stimulation testing.

Female participants will specifically be queried regarding abnormal vaginal bleeding (new and different from any related to any known EB wounds in the genital area), new breast findings (not related to EB wounds), expulsion of an intrauterine device or implant, or vaginal discharge. If any of these concerns are identified, the participant will be referred to their primary care provider for further evaluation.

9.F.iii. Assessments via REDCap:

A link will be sent to the participant to complete the following assessments via REDCap:

1. Stanford EB Itch Survey
2. Itch Man
